6.3 Depth of Sedation

During induction and recovery the depth of sedation will be assessed using the University of Michigan Sedation Scale (UMSS).

Table 2: University of Michigan Sedation Scale

- Awake/Alert
- 2. Minimally Sedated: Tired/sleepy, appropriate response to verbal conversation and/or sounds
- 3. Moderately Sedated: Somnolent/sleeping, easily aroused with light tactile stimulation
- 4. Deeply Sedated: Deep sleep, aroused only with significant physical stimulation
- 5. Unarousable

The UMSS is an observational tool that scores the patient's responsiveness to stimuli in a manner consistent with nationally recognized definitions and was found to have a moderate to high correlation with BIS monitoring in children under 18 years old. [7]

6.4 Maintenance of anesthesia

Anesthesia will be maintained using the standard clinical practice and at the discretion of the anesthesiologist.

6.5 Anesthesia Recovery

During recovery in the PACU, EEG and other physiological data will be collected (if patient's tolerance permits it).

. Data collection may be terminated during this time period at the PI's and/or designated research staff's discretion.

6.6 Excluded Medications and Treatments

There are no excluded medications or treatments for this study.

6.7 Measurements

EEG waveforms will be collected from the SedLine module and Neuroscan Data Acquisition System and anesthesia record with concomitant medications. Additionally, head size and vital signs such as heart rate, respiratory rate, blood pressure, temperature, and oxygen saturation will be collected using FDA approved monitors and/or standard of care (SOC) monitors.

7 SAMPLE SIZE AND STATISTICAL CONSIDERATIONS

The purpose of data collection is an observational study to build a database of representative PSI signal profiles for the pediatric population under select conditions. Sample size is therefore non-deterministic by normal

sampling means. Approximately 220 subjects will be enrolled in the study. Site should do its best to achieve sufficient enrollment in all age groups.

Age		
12 months and		
younger		
13-35 months		
3-5 years		
5-11 years		
11-17 years		

8 SAFETY AND ADVERSE EVENTS

8.1 Definitions

The definitions for adverse event, adverse device effect, serious adverse event, serious adverse device effect, and unanticipated adverse device effect are provided below (ISO 14155:2011, 21 CFR 812.3(s)).

- Adverse Event (AE): an adverse event is any untoward medical occurrence in a subject which need not be related to the device under investigation.
- Adverse Device Effect (ADE): an adverse device effect is any untoward or unintended response to a
 medical device which may result from insufficiencies in the instructions for use or deployment of the
 device, or from use error.
- Serious Adverse Event (SAE): a serious adverse event is an adverse event that results in death, inpatient
 hospitalization, severe or permanent disability, a life threatening illness or injury, fetal distress, fetal
 death, a congenital abnormality, a birth defect, or medical or surgical intervention to prevent
 permanent impairment to body or structure.
- Serious Adverse Device Effect (SADE): a serious adverse device effect is an adverse device effect that results in death, inpatient hospitalization, severe or permanent disability or is life threatening.
- Unanticipated Adverse Device Effect (UADE): any serious adverse effect on health or safety or any life
 threatening problem or death cause by or associated with, a device, if the effect, problem, or death was
 not previously identified in nature, severity or degree of incidence in the investigational plan, or
 application (including a supplementary plan or application) or any other unanticipated serious problem
 associated with a device that related to the rights, safety or welfare of subjects. Refer to the Device Risk
 Analysis and Risk Assessment section for details on anticipated adverse device effects.

8.2 Anticipated Adverse Events:

Mild allergic reaction to sensor material and adhesives.

8.3 Adverse Event Reporting:

- All Adverse Events, both Anticipated and Unanticipated, must be recorded in the CRF and recorded in detail in the Adverse Event Report Form.
- All Adverse Events must be promptly reported to the Sponsor.
- All Unanticipated Adverse Device Effects will be also reported to both the Sponsor and the IRB.

- Both Serious Adverse Events and Unanticipated Adverse Device Effects must be reported to the Sponsor within 48 hours. All other Adverse Events should be reported to the Sponsor within 5 business days.
- All Serious Adverse Events will be also reported to the IRB per IRB reporting requirements. These
 reports may include, but will not be limited to: date of onset; brief description of the events; their
 treatment; whether they resulted in death, inpatient hospitalization, severe or permanent disability or
 were life threatening; their relationship to the study device; and resolution.

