10 MONITORING PLAN

- 10.1 As the sponsor of this clinical investigation, Masimo Corporation is required by 21 CFR, Part 812, of the Food and Drug Administration regulations to monitor and oversee the progress of the investigation. The monitor(s) assigned by Masimo Corporation to this task will be employee(s) from the Clinical Research department who are trained on departmental SOPs and have adequate experience in conducting monitoring visits.
- 10.2 In accordance with good clinical practices guidelines, there will be at least three scheduled monitoring visits to ensure overall regulatory compliance of the study:
 - An initiation visit, prior to any subject enrollment to confirm site readiness, and to document training on the study protocol and procedures, and use of equipment.
 - At least one monitoring visit during enrollment, preferably when enrollment has reached 10% of subjects, and then at least once every 6 months thereafter.
 - A final close out visit after the last patient had finished the study.
- 10.3 Study monitor(s) will initiate contact and setup on-site visits with the investigator. Study monitor(s) will be allowed, on request, access to all source documents needed to verify the entries in the CRFs and to all other GCP-related documents (IRB approvals, IRB correspondences, and ICFs) provided that subject confidentiality is maintained in agreement with HIPAA regulations.
- 10.4 It will be the monitor's responsibility to inspect the CRFs at regular intervals throughout the study, to verify the adherence to the CIP and the completeness, consistency and accuracy of the data being entered on them.
- 10.5 During each visit, the monitor will also verify presence of informed consent, adherence to the inclusion/exclusion criteria, and documentation of SAEs/SADEs and protocol deviations/violations, and check CRF against source documentation.

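### Section 8.1 makes an event serious if it causes an admission but not if it lengthens one, and its SADE list omits a criterion that the SAE list contains

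*Combined protocol and SAP*

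**What the plan says.** Section 8.1 builds seriousness in two layers. The entry condition is the AE definition: "an adverse event is any untoward medical occurrence in a subject which need not be related to the device under investigation". The SAE definition then requires a causal link to a listed outcome. It opens with "a serious adverse event is an adverse event that results in death, inpatient", continues with "hospitalization, severe or permanent disability, a life threatening illness or injury, fetal distress", and ends with fetal "death, a congenital abnormality, a birth defect, or medical or surgical intervention to prevent" permanent impairment of body or structure. Being admitted as an inpatient is the only hospital-related outcome.

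The device counterpart is shorter: "a serious adverse device effect is an adverse device effect that results in death, inpatient hospitalization, severe or permanent disability or is life threatening".

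Section 8.3 attaches consequences to these labels. SAEs and UADEs go to the sponsor within 48 hours. For the rest, "All other Adverse Events should be reported to the Sponsor within 5 business days". SAEs also go to the IRB under the IRB's own requirements, and UADEs go to both sponsor and IRB. The suggested content of an SAE report in 8.3 again names inpatient hospitalization, without prolongation. Section 10.5 has the monitor verify "documentation of SAEs/SADEs and protocol deviations/violations".

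On population, Section 4.2 admits ASA I to III children aged 17 or younger who are scheduled for surgical or non-surgical procedures under anesthesia or sedation. Section 4.3 has no exclusion for children who are already inpatients.

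**The concern.** In a study carried out around procedures, some of the children may already be in hospital or be due to stay. For such a child, a complication usually shows its cost as extra days and not as a new admission. A definition that counts only admission then classifies by bed status: two children with the same complication can receive different labels because one was a day case and the other was not.

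The label matters because it sets the sponsor's reporting deadline and decides whether the event has a stated SAE route to the IRB. Section 11 plans no data and safety monitoring board, so sponsor and IRB reporting carry most of the oversight of an investigational pediatric sensor.

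The second issue is consistency. SAE and SADE should use the same test of seriousness and differ only in relation to the device. Here the tests differ, so a serious device-related injury can be counted under one heading and not the other.

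**Working it through.** The plan states no figure on this point, so the check compares the definitions and traces what each label triggers.

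**Step 1: is prolongation covered anywhere?** Neither the SAE definition and the SADE definition in 8.1 nor the report content in 8.3 mentions it. No other section of the available text does either. That text passes from Section 2 to Section 4, so the finding covers what could be read.

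**Step 2: one complication, two children.** Assume the complication is not life threatening, leaves no disability and needs no intervention to avert permanent impairment.

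| | Day-case child, now admitted | Child already admitted, stay lengthened |
|---|---|---|
| Untoward occurrence (AE)? | Yes | Yes |
| Results in inpatient admission? | Yes | No, the admission came first |
| Label under 8.1 | SAE | Non-serious AE |
| Outer limit to sponsor (8.3) | 48 hours | 5 business days |
| SAE route to IRB (8.3) | Yes | No |

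If any other listed criterion is met, both children's events are SAEs and the difference disappears.

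**Step 3: size of the delay.** 48 hours is 2 calendar days. Five business days that span one weekend are 5 + 2 = 7 calendar days. The outer limit moves by 7 − 2 = 5 calendar days.

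**Step 4: SAE list against SADE list.** The SAE definition has nine outcomes: death, inpatient admission, severe or permanent disability, life-threatening illness or injury, fetal distress, fetal death, congenital abnormality, birth defect, and intervention to prevent permanent impairment. The SADE definition has four: death, inpatient admission, severe or permanent disability, and life-threatening. So 9 − 4 = 5 are missing. Four of these are fetal or congenital and matter little in a pediatric study. The fifth, the intervention criterion, is the omission of substance.

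**Step 5: does the SADE gap alter reporting?** Take a device injury that is an untoward occurrence and needs intervention to avert permanent impairment. It is an SAE under 8.1, so it reaches the sponsor in 48 hours and goes to the IRB. No rule in 8.3 depends on SADE status. The gap changes the label and not the clock.

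**Step 6: how many events?** The prolongation gap matters only for a child who is already an inpatient, has an adverse event, stays longer because of it, and meets no other seriousness criterion. The documents give no rate for any of these four conditions, so the number cannot be calculated.

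**The case against.** The case for leaving the text alone has real weight.

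- **Nothing goes unreported.** Section 8.3 requires every adverse event to be recorded and promptly reported to the sponsor, so 5 business days is an outer limit. Section 14 has the investigator evaluate all adverse events. The gravest events, including life-threatening ones and those needing intervention to avert impairment, are already SAEs. This stands and limits the consequence.
- **Few events may be seen.** Under Section 4.4 the visit ends when the child wakes in the PACU, and data collection is then complete. A longer stay usually becomes apparent later. The only anticipated event in 8.2 is a mild allergic reaction to the sensor. This also stands. It argues for a low severity, but it does not make the definition right.
- **The SADE gap changes no deadline.** Step 5 agrees. What remains is an inconsistent classification.

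Three stronger readings might tempt a reader, and the documents do not support them:

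- *That the definition sweeps in planned admissions.* It does not. The admission must result from an untoward occurrence, and a scheduled admission is neither untoward nor the result of one. At most, a clarifying sentence is absent.
- *That the SAE wording controls entry to the UADE category.* The UADE definition has its own language on serious effects and serious problems and does not refer to the SAE or SADE list. A serious, unanticipated device effect that lengthens a stay can still be a UADE, with its 48-hour limit and IRB reporting.
- *That the rule is wrong for dozens of children.* An assumed inpatient share of 10% to 40% of the 220 subjects gives 220 × 0.10 = 22 to 220 × 0.40 = 88. The share is not in the documents, and the result counts children who might be inpatients, not misclassified events. Affected events are those left after the further conditions in Step 6.

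**Conclusion.** The point holds, and its severity is minor. On a literal reading, Section 8.1 treats the same complication as serious in a child who has to be admitted and as non-serious in a child whose existing stay is extended. The effect is an outer reporting limit about 5 calendar days longer and the loss of the SAE route to the IRB. It does not apply when another seriousness criterion is met or when the event qualifies as a UADE. The number affected is unknown and probably small.

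Separately, the SADE list is narrower than the SAE list in one respect that matters. The result is inconsistent labelling of a serious device injury, with its 48-hour deadline intact.

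The conclusion rests on two assumptions: that some enrolled children are inpatients, which eligibility permits but does not state, and that sites apply the definition as written.

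**What to change.** Two edits, with matching wording on the case report and adverse event forms:

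1. Add *or prolongation of existing hospitalization* after inpatient hospitalization in the SAE definition in 8.1, and make the same addition to the SAE report content in 8.3.
2. Define a SADE in 8.1 as an adverse device effect that meets any SAE criterion. The two lists then cannot diverge, and the SADE definition takes up prolongation automatically.

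Two optional sentences would help: one confirming that an admission planned before enrollment is not in itself an SAE, and one stating until when adverse events are collected. The available text gives no such window, and without one the first edit may capture few events.

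The cost is a short amendment and possibly a few more 48-hour reports. No study procedure or data collection for the EEG objective changes.

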8.4 Deviations from the study protocol

Deviations from the protocol must receive both Sponsor and the investigator's IRB approval before they are initiated. Any protocol deviations initiated without Sponsor and the investigator's IRB approval that may affect the scientific soundness of the study, or affect the rights, safety, or welfare of study subjects, must be reported to the Sponsor and to the investigator's IRB as soon as a possible, but no later than 5 working days of the protocol deviation.

8.5 Withdrawal of IRB approval

An investigator shall report to the sponsor a withdrawal of approval by the investigator's reviewing IRB as soon as a possible, but no later than 5 working days of the IRB notification of withdrawal of approval.

9 DATA MANAGEMENT

9.1 Provisions to Protect the Privacy Interests of Subjects

Potential study candidates will be identified following a review of the elective surgical schedule. The attending surgeon will then be contacted to confirm the appropriateness of the patient and identify any steps that are indicated to protect the subjects' privacy interests. Patient recruitment and informed consent will be obtained when there is sufficient time for a complete discussion between the investigator and the patient. Recruitment will be by direct discussion between the prospective candidates and the study investigators prior to their scheduled surgical procedure. The investigators and/or designated study staff will provide the consent form in person and give the prospective subject sufficient time to review the consent form and discuss the study with friends and family.

9.2 Data Management and Confidentiality

All documents associated with this protocol will be kept in the locked offices or on password protected computers. All data will be de-identified before any statistical analysis. Only de-identified data will be shared with Masimo for research purposes stated in this clinical investigation plan. Data collected by data capture software and data entered in case report form will be shared with Masimo via a secure, password protected server that only study staff and Masimo study team members will have access to. Blood specimens, if any are required per current clinical investigation plan, will be handled according to standard procedures for biological materials. Data will be retained for up to 2 years following completion of the final analysis.

9.3 Source Documents

Source data is all information, original records of clinical findings, observations, or other activities in a clinical trial necessary for the reconstruction and evaluation of the trial. Source data are contained in source documents. Examples of these original documents and data records include: hospital records, clinical and office

charts, laboratory notes, memoranda, recorded data from automated instruments, and copies or transcriptions certified after verification as being accurate and complete.

9.4 Screening and Enrollment Logs

A subject screening and enrollment log will be provided to study site by sponsor, and maintained by study site. The screening and enrollment log will document, at a minimum, information such as the number of subjects approached for informed consent, the date of consent, subject eligibility, subject enrollment status, subject withdraw (if applicable) and reason(s) for withdrawal.

9.5 Case Report Forms

- 9.5.1 The Sponsor shall provide a Case Report Form (CRF) template to the Site. The Site shall capture study data in the CRFs for each subject enrolled. The CRFs will be reviewed and signed by principal investigator. This also applies to those subjects who fail to complete the study. If a subject withdraws from the study, it is highly recommended that the reason(s) be noted on the CRF. Case report forms are to be completed on an ongoing basis. CRF entries and corrections will only be performed by study site staffs that are authorized by the investigator. Entries and corrections to the CRF will be made following Good Documentation Practices.
- 9.5.2 The CRF will include the following information, including but not limited to: inclusion / exclusion criteria, whether patient consent obtained before start of study, demographic information, event timing, anesthetic drugs used and dosage, patient skin condition after sensor removal, etc.
- 9.5.3 The CRF will be signed by the PI, and securely transferred to Masimo in pdf format.
- 9.5.4 CRF entries will be checked by Sponsor personnel after receipt and any errors or inconsistencies will be queried to the site on an ongoing basis. Query resolution will be assessed and confirmed by study monitor during site visit.

9.6 Data Transfer and Storage

- 9.6.1 Device data will be captured through data capture software (Pulse-Ox Automated Data Collection and Rugloop) and stored on a laptop. Device data along with a pdf copy of the CRF will be uploaded to sponsor via secure FTP portal after each study visit completion.
- 9.6.2 Only authorized sponsor personnel will have access to the uploaded data on the secure FTP portal, and will move it to a secure and backed-up drive at Masimo after receiving the upload from study site.
- 9.6.3 Device data and pdf copies of CRFs will be checked for completeness. If there are inconsistent or missing data points, a data query list will be generated and submitted to the site for corrections. Once all queries have been resolved, Masimo engineers are notified that data is ready for analysis. To ensure data integrity, Masimo engineers will only have read access to the location where data is being securely stored, therefore are unable to unintentionally tamper with the original data files.

9.7 Record Retention

Study data will be retained for the necessary period of time as required by the institution's regulations. Study Records shall be retained for a minimum of two years after study closure. The Institution's own retention policies and regulations may apply in addition to the minimal requirement.

10 MONITORING PLAN

- 10.1 As the sponsor of this clinical investigation, Masimo Corporation is required by 21 CFR, Part 812, of the Food and Drug Administration regulations to monitor and oversee the progress of the investigation. The monitor(s) assigned by Masimo Corporation to this task will be employee(s) from the Clinical Research department who are trained on departmental SOPs and have adequate experience in conducting monitoring visits.
- 10.2 In accordance with good clinical practices guidelines, there will be at least three scheduled monitoring visits to ensure overall regulatory compliance of the study:
 - An initiation visit, prior to any subject enrollment to confirm site readiness, and to document training on the study protocol and procedures, and use of equipment.
 - At least one monitoring visit during enrollment, preferably when enrollment has reached 10% of subjects, and then at least once every 6 months thereafter.
 - A final close out visit after the last patient had finished the study.
- 10.3 Study monitor(s) will initiate contact and setup on-site visits with the investigator. Study monitor(s) will be allowed, on request, access to all source documents needed to verify the entries in the CRFs and to all other GCP-related documents (IRB approvals, IRB correspondences, and ICFs) provided that subject confidentiality is maintained in agreement with HIPAA regulations.
- 10.4 It will be the monitor's responsibility to inspect the CRFs at regular intervals throughout the study, to verify the adherence to the CIP and the completeness, consistency and accuracy of the data being entered on them.
- 10.5 During each visit, the monitor will also verify presence of informed consent, adherence to the inclusion/exclusion criteria, and documentation of SAEs/SADEs and protocol deviations/violations, and check CRF against source documentation.
- 10.6 After each visit, the monitor will provide a monitoring report to the investigator within 4 weeks of visit completion. The monitoring report will detail findings and open action items observed during the visit. It is the responsibility of the Principal Investigator and Study Coordinator(s) to respond to the findings of the monitoring report, and complete any open action items as soon as possible but no later than 60 days of receiving the monitoring report. Any open action items not completed within the time allowed may be sufficient grounds for study site suspension or termination; it will be up to the sponsor to determine whether any incomplete action items are sufficient grounds for suspension or termination. See Section 13 for details on suspension and termination.

10.7 Depending on the quality of the data and/or changes to factors affecting patient safety, additional monitoring visits may be necessary at the sponsor's discretion.

